**Brief Intervention for Justice-Involved Substance Users:
Harnessing Mechanisms of Change**

NCT03308877

04/01/2017

Study Design

D.3. Overview. We propose a rigorous RCT using a matched-pairs design to test *a priori* hypotheses based on the findings of Preliminary Study 2, while investigating the mechanisms by which people change. In line with renewed national efforts to promote reproducible science, this study is, among other things, an attempt to replicate the primary findings of our published work in a larger sample. We incorporate appropriate blinding, and validated, multi-method measurement of constructs. We will compare the efficacy of BMI+SC versus SC across two groups: a) individuals with low/moderate affective psychopathy (affective score < 5) and, b) individuals with high affective psychopathy (affective score > 5). In Session One, individuals who are within their first three weeks at MCPS will be recruited and briefly screened for substance use. Individuals who report substance use once per week or more and meet the Drug Abuse Screening Test cutoff score of 3 or higher⁵¹ will continue in the study. Session Two (Baseline Assessment A) will involve a brief assessment of general psychopathology and detailed assessment of psychopathy and frequency of use of a range of substances. Baseline assessment B will include assessment of putative mediators (self-regulation and commitment to change), along with an assessment of treatment services use over the past 6 months. After Baseline Assessment B, participants will be randomized (coin toss) to either BMI+SC or SC in pairs that are matched according to affective psychopathy level. That is, two individuals with low/moderate affective psychopathy will be randomized (one each) to either BMI+SC or SC. The same will occur with individuals who are high in affective psychopathy. The next session will occur as close to baseline as possible, followed by sessions at 2, 4, and 6 weeks post-baseline. These meetings will involve assessments of frequency and type of substance use (both groups), and the delivery of our BMI (treatment group only). The outcome variables will be 1) frequency of substance use (proximal; percent days abstinent at 6 months) and 2) violent criminal recidivism (distal; charges at 12 months).

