**Brief Intervention for Justice-Involved Substance Users:
Harnessing Mechanisms of Change**

NCT03308877

04/01/2017

D.7. Data Analysis. A baseline check of randomness will be conducted for each variable collected. Categorical variables will be analyzed using chi-square tests; continuous variables with ANOVAs. To assess Hypothesis 1 continuous outcomes, Analysis of Covariance will be used. The effects of BMI+SC on commitment to change, self-regulation, and substance use will be assessed immediately following intervention. Longer term substance use effects will be examined at 6-month follow-up. For substance use toxicology results, logistic regression will be used. In all instances, alpha = .05; covariates will include gender, race, age, and the outcome baseline score of interest as well as any other variables found to differ at baseline. Additionally, effect sizes will be examined using marginal means.⁷¹ Structural equation modeling (SEM) will be used to test the hypothesis that the effect of BMI+SC on substance use will be mediated by increases in commitment to change and self-regulation (Figure 2).⁷² *Substance use status* at six month follow-up is the key outcome of interest. We hypothesize that effects on six month substance use are mediated, in part, by BMI+SC effects on commitment to change and self-regulation. Substance use status will be measured using two indicators, percent days abstinent and the urine screen result. *Commitment to Change* will be measured using two indicators at each time point, the Readiness Ruler and the CLEAR change talk score at both baseline and immediate post. Two indicators will also be used to assess *Self-Regulation* at baseline and immediate post: Self-Regulation Questionnaire scores and Balloon Analog Risk Task scores. Additionally, demographic variables will be statistically controlled for in the model (gender, age, race, ethnicity). The MPLUS statistical package⁷³ will be used for SEMs. To provide a metric for each latent construct and to identify the model, the first construct loading for each latent variable will be set at 1.0. A two-step approach examining the model will be undertaken.⁷⁴ First, using confirmatory factor analytic techniques, a test of the proposed measurement model will be conducted and any needed modifications to this model, including testing for measurement invariance over time, will be undertaken prior to examining model fit. The second step involves an examination of the structural portion of the model. The model suggests that BMI effects on substance use are not only direct, but also indirect, mediated by effects on commitment to change and self-regulation. Baseline substance use status, commitment to change, and self-regulation will be controlled for, aiding precision in detecting treatment effects. Fit of the model will be assessed using a chi-square statistic, as well as the more approximate fit indices of the root mean square error of approximation (RMSEA),⁷⁵ the comparative fit index (CFI),⁷⁶ and the standardized root mean square residual (SRMR). Using various cutoffs for fit assessment helps to minimize Type I and Type II errors.⁷⁷ Recommendations that adequate fitting models have $CFI > .95$, $RMSEA < .06$, and $SRMR < .08$ will be adopted here. BMI indirect effects on 6 month substance use will be tested using the bias-corrected confidence limits.⁷⁸ Significance will be assessed by whether or not the 95% confidence limits contain zero. The bias corrected approach has been shown to provide the most accurate confidence limits and greatest statistical power when compared with other existing approaches for detecting mediation.⁷⁸ Multi-group structural equation modeling will be used to test moderated mediation. Two groups (high vs. low/moderate on affective psychopathy) will be compared. We will isolate differences across models by first examining if measurement parameters are equal across groups. Model differences across groups will be tested using the chi-square difference test. Next, we will test for structural differences across groups, examining regression parameter estimates for equality, followed by an examination of latent variables' variances and means across the groups. Such moderated-mediation will allow for isolation of BMI effects on latent variable means, controlling for process differences across the groups. Four exploratory analyses will also be conducted. The first will examine longitudinal change in substance abuse using growth curve analyses. Substance use is measured at baseline, 4 times during the intervention period, and at 6-month follow-up (6 time points). Time will be modeled so that the intercept reflects baseline status and subsequent time points will be modeled as weeks from baseline. Both linear and curvilinear (quadratic) change

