
will be examined using the same covariates as previously mentioned. Here, we are interested in the time by condition interaction term, addressing whether the trajectory of substance use differs across the BMI+SC and SC groups. Second, we will determine whether BMI+SC had an effect on violent recidivism using logistic regression. We will also use the structural equation models above to examine mediational and moderated mediation effects of BMI on violent recidivism. Finally, we will also examine the moderated mediation models across gender and race (white vs. black) to determine if mean and/or process differences exist for males and females as well as for White and Black participants. (Numbers of other races/ethnicities are likely to be too low for separate analysis).

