D.7.1 Power, Missing Data, and Type 1 Error Protection. For analyses involving continuous mean differences Optimal Design software was used to assess statistical power. With a sample size of 416, we are adequately powered ($> .80$) to detect a small standardized effect with baseline covariates explaining 40% of the outcome variance (n required = 265 to achieve .80 power). Should baseline covariates explain only 30% of the variance, we are powered at .78 to detect small effects. The inclusion of baseline covariates typically improves precision (at the cost of degrees of freedom)⁷⁹ For the logistic analyses predicting urine screen substance use results and 12-month recidivism, power analyses were conducted using the Stata statistical software program. We are interested in the power of treatment status to significantly detect a difference in positive urine screens and violent recidivism by 12 months. In a likely scenario of 50% positive urine screens, we are adequately powered (.80) to detect a 14% or more difference in rates. Power improves slightly as the baseline rates drift away from 50%. Typical 12-month violent recidivism rates are 20%. Here, we are adequately powered to detect a 12% point difference in rates, even if average absolute baseline covariate correlation with treatment is .3. For the structural equation model to be tested,⁸⁰ our approach allows for the testing of a null hypothesis of not good fit, reversing the role of the null hypothesis in conventional tests of model fit, so that a significant result provides strong support for good fit. With an expected sample size of 416, adequate power ($> .95$) to reject an hypothesis of close fit ($RMSEA > .08$) with 94 degrees of freedom (df) given a population $RMSEA$ of .05 was obtained (proposed model including age, gender, 2 race variable = 94 df). Additionally, adequate power (.99) to reject a hypothesis of not-close fit was obtained. Here, if model fit is extremely good ($RMSEA < .01$), and we test the hypothesis that fit is not close, we have greater than .95 power to reject the null hypothesis that $RMSEA > .05$. Even if sample size drops to 300, power for both the hypothesis of close fit and the hypothesis of not close fit remains above .90. As more degrees of freedom are introduced with the addition of multi-group modeling (psychopathy, gender, race), power improves on the above estimates. For analyses examining mean and rate differences, pairwise deletion of missing data will be used, thus retaining all available information. As a form of sensitivity analysis, however, multiple imputation of missing data will be conducted, which has consistently demonstrated less biased parameter estimates than most other approaches to the handling of missing data.⁸¹ To help control for Type 1 error, the Benjamini-Hochberg (BH) method⁸² will be used to adjust for the multiple comparisons proposed. The BH method adjusts for multiple comparisons by controlling the false discovery rate instead of family-wise error rate. It is less conservative than the more traditional Bonferroni methods, yet still provides adequate protection against Type 1 error.

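### Stated power for the mean and rate comparisons makes no allowance for the planned Benjamini-Hochberg adjustment, and the set of tests to be adjusted is not fixed

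*SAP*

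**What the plan says.** SAP D.7 sets the significance level for the ANCOVA and logistic tests: "In all instances, alpha = .05". SAP D.7.1 adds that BH "will be used to adjust for the multiple comparisons proposed", and describes it as "controlling the false discovery rate instead of family-wise error rate". It states no false discovery rate level (q), no family and no number of tests (m).

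The power paragraph of D.7.1 names no significance level and does not refer to BH. For continuous outcomes it says "With a sample size of 416, we are adequately powered" for a standardized effect described only as small. For urine screens it claims .80 power for a 14-point difference from 50%. For 12-month violent recidivism it claims adequate power for 12 points from a 20% rate.

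For the indirect effects in the mediation model, D.7 uses a different rule: "Significance will be assessed by whether or not the 95% confidence limits contain zero".

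On the rank of recidivism, Protocol D.3 reads: "The outcome variables will be 1) frequency of substance use (proximal; percent days abstinent at 6 months) and 2) violent criminal recidivism". SAP D.7 puts the same endpoint second among four analyses it labels exploratory: "Second, we will determine whether BMI+SC had an effect on violent recidivism using logistic regression". D.7 names six-month substance use status as its key outcome, measured by percent days abstinent and the urine result.

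**The concern.** BH compares the k-th smallest p-value with k × q / m, so it cannot be run until q and the family are fixed. Any test in the family may have to meet a threshold below .05. If power was calculated at .05, it describes an easier test than the one planned.

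The open family also leaves room for choice after the data are seen. Take p = .02 for 6-month percent days abstinent, with q = .05 and no other rejection. In a family of two the first step is .05/2 = .025 and the result passes. In a family of four it is .05/4 = .0125 and the result fails. Protocol D.3 presents the trial as an attempt to replicate earlier findings through pre-specified hypotheses, so that choice should be closed in advance.

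**Working it through.** **Inputs.** From the documents: 416 analysed; pairs in which two people "will be randomized (one each) to either BMI+SC or SC", so 208 per arm; 50% positive screens and a 14-point difference; 20% recidivism and a 12-point difference; covariates explaining 40% or 30% of variance. Assumed, because not stated: two-sided tests, q = .05, m = 4 to 8, and the numerical size of a small effect. The range for m is plausible. D.7 alone proposes tests of commitment, self-regulation and substance use after the intervention, substance use at 6 months, and toxicology. That is five before mediation, moderation or recidivism.

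**Step 1: reproduce the urine figure.** With n = 208, p1 = .50, p2 = .36 and mean rate .43:

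- Standard error under no difference: sqrt(2 × .43 × .57 / 208) = .04855
- Standard error under the alternative: sqrt((.25 + .2304) / 208) = .04806
- Power with continuity correction: Φ[(.14 − 1/208 − 1.960 × .04855) / .04806] = Φ(.833) = .798

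This matches .80. Without the correction the result is .825; one-sided it is .895; at two-sided .01 it is .622. The figure fits an unadjusted two-sided .05.

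**Step 2: the same comparison at the strictest BH step, .05/m.** Replacing 1.960 by the critical value for .05/m gives .61 (m = 4), .56 (m = 6) and .52 (m = 8). Regaining .80 at that step needs 584 analysed for m = 4 or 632 for m = 6, against 420 at .05.

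**Step 3: full BH rather than the strictest step.** Simulation with 200,000 runs per setting, q = .05, every true effect having .80 unadjusted power, and correlation 0 or .3 between tests:

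| m | only this effect true | half true | all true |
|---|---|---|---|
| 4 | .63 | .69 | .76-.77 |
| 6 | .57 | .67-.68 | .76-.77 |
| 8 | .53 | .66-.68 | .75-.77 |

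**Step 4: recidivism.** No continuity correction; the covariate correlation of .3 is taken as a variance inflation with R² = .09. For 20% v 8%, power is .92 at .05, .81 at .05/4 and .77 at .05/6. For 20% v 32%, it is .76, .57 and .51.

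**Step 5: continuous outcomes.** With R² = .40, SE = sqrt(4 × .60 / 416) = .0760 and power = Φ(d/SE − z). D.7.1 gives no d. Its n of 265 for .80 power at R² = .40 implies d = (1.960 + .842) × sqrt(4 × .60 / 265) = 0.267. Its .78 power at R² = .30 implies d = (1.960 + .772) × sqrt(4 × .70 / 416) = 0.224. A conventional d = 0.2 is shown as an assumption.

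| d | power at .05 | at .05/4 |
|---|---|---|
| 0.2 | .75 | .55 |
| 0.224 | .84 | .67 |
| 0.267 | .94 | .85 |

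**Step 6: model fit.** The RMSEA power statements concern fit of the structural model, not a treatment comparison. They recompute above .99 at 416, and at .996 and .986 at 300.

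**The case against.** A reader might infer that a level of .05 in all instances contradicts BH. It does not: .05 can be the level at which BH-adjusted p-values are judged. The gap is that the SAP does not say so.

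A reader might also infer that the stated power does not apply at all. That goes too far. BH is milder than Bonferroni, and if all effects are real the loss is only 3 to 5 points. The strictest-step figures are a worst case. For continuous outcomes, the d = 0.267 implied by the SAP's own n of 265 still gives .81 at .05/6. Setting the .55 for d = 0.2 against the SAP's claim of more than .80 would charge multiplicity with a shortfall that starts from an assumed effect size; power is already .75 with no adjustment. That the two SAP figures imply different effects is a separate matter.

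Nor does judging mediation by confidence limits keep those tests out of BH for good, since bootstrap p-values can be computed. Calling recidivism an outcome in one document and exploratory in the other changes no power figure by itself, and adding a test that is rejected can loosen the cutoff for the others. Its rank matters only through membership of the family.

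Finally, making one contrast primary is a choice. D.7's key outcome has two indicators, D.3 frames the comparison across two affective-psychopathy groups, and the wording of Hypothesis 1 is not in the text available. This stands as a reason for the sponsor to confirm the choice.

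These points narrow the claim. They do not explain power figures that leave out an adjustment the same section prescribes.

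**Conclusion.** The concern holds in a limited form. The stated power for mean and rate comparisons is an upper bound under the plan's own testing rule. The evidence is firmest for the urine screen, where .80 is reproduced at an unadjusted two-sided .05. With q = .05 and 4 to 8 tests, both assumed, such a test falls to between .53 and .77, depending mainly on how many other effects are real. For continuous outcomes the consequence cannot be fixed until the small effect has a number. Power for model fit stands.

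The undefined family is part of the same problem. Indirect effects have an unadjusted rule beside a promised adjustment, and recidivism has two ranks. A missing q or list alone would be a matter of detail. Together with the power mismatch it should be settled before analysis.

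**What to change.** 1. Name the BMI+SC v SC difference in 6-month percent days abstinent as the primary test, at two-sided .05 and outside BH. The sponsor should first confirm that this fits Hypothesis 1 and the affective-psychopathy question. An unadjusted power calculation is then the right one for that test; state the d it uses.
2. Apply BH at a stated q, for example .05, to a listed secondary family: urine result, commitment to change, self-regulation, indirect effects (with bootstrap p-values), affective-group moderation and violent recidivism. Say that analyses outside the list are exploratory and unadjusted.
3. Give violent recidivism one rank, the same in both documents.
4. Keep .05, but say where it is the per-test level and where it is the false discovery rate level.
5. Restate urine and recidivism power as unadjusted upper bounds, or recompute it under BH with the assumed number of true effects.

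The cost is wording, with no new data or participants. Secondary tests become somewhat harder to pass, and their stated power will look less favourable.
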